8.0 Inclusion and Exclusion Criteria*

8.1 *Describe the criteria that define who will be **included** in your final study sample.*

NOTE: This may be done in bullet point fashion.

1) adults (>18 years), 2) PH confirmed by standard guidelines; 3) willingness to participate in the mindfulness practice program for the duration of the study period; 4) able to ambulate independently; 5) English-speaking, and 6) have access to a mobile phone.

8.2 *Describe the criteria that define who will be **excluded** from your final study sample.*

NOTE: This may be done in bullet point fashion.

1) known pregnancy; 2) have psychiatric conditions requiring hospitalization within the last year; 3) deaf or hard of hearing.

8.3 *Indicate specifically whether you will include any of the following special populations in your study using the checkboxes below.*

NOTE: Members of special populations may not be targeted for enrollment in your study unless you indicate this in your inclusion criteria.

Response:

- Adults unable to consent
- Individuals who are not yet adults (infants, children, teenagers)
- Pregnant women
- Prisoners

8.4 Indicate whether you will include non-English speaking individuals in your study. **Provide justification if you will exclude non-English speaking individuals.**

*In order to meet one of the primary ethical principles of equitable selection of subjects, non-English speaking individuals may **not** be routinely excluded from research as a matter of convenience.*

In cases where the research is of therapeutic intent or is designed to investigate areas that would necessarily require certain populations who may not speak English, the researcher is required to make efforts to recruit and include non-English speaking individuals. However, there are studies in which it would be reasonable to limit subjects to those who speak English. Some examples include pilot studies, small unfunded studies with validated instruments not available in other languages, studies with numerous questionnaires, and some non-therapeutic studies which offer no direct benefit.

The study will exclude non-English speaking individuals because the questionnaires used to obtain data are available in English format. Furthermore, the intervention will be delivered in the English language only.

9.0 Vulnerable Populations*

If the research involves special populations that are considered vulnerable, describe the safeguards included to protect their rights and welfare.

NOTE: You should refer to the appropriate checklists, referenced below, to ensure you have provided adequate detail regarding safeguards and protections. You do not, however, need to provide these checklists to the IRB.

9.1 For research that involves **pregnant women**, safeguards include:
NOTE CHECKLIST: Pregnant Women (HRP-412)

Response:

N/A: This research does not involve pregnant women.

9.2 For research that involves **neonates of uncertain viability or non-viable neonates**, safeguards include:

NOTE CHECKLISTS: Non-Viable Neonates (HRP-413), or Neonates of Uncertain Viability (HRP-414)

Response:

N/A: This research does not involve non-viable neonates or neonates of uncertain viability.

9.3 For research that involves **prisoners**, safeguards include:

NOTE CHECKLIST: Prisoners (HRP-415)

Response:

N/A: This research does not involve prisoners.

9.4 *For research that involves persons who have not attained the legal age for consent to treatments or procedures involved in the research ("children"), safeguards include:*

NOTE CHECKLIST: Children (HRP-416)

Response:

N/A: This research does not involve persons who have not attained the legal age for consent to treatments or procedures ("children").

9.5 *For research that involves cognitively impaired adults, safeguards include:*

NOTE CHECKLIST: Cognitively Impaired Adults (HRP-417)

Response:

N/A: This research does not involve cognitively impaired adults.

9.6 *Consider if other specifically targeted populations such as students, employees of a specific firm, or educationally or economically disadvantaged persons are vulnerable. Provide information regarding their safeguards and protections, including safeguards to eliminate coercion or undue influence.*

Our target population is adults with PH living throughout the United States. There is a high likelihood that our study participants may include economically disadvantaged persons. The study recruitment and enrollment process will occur in collaboration with PH doctors and nurses from these 3 locations and across the country who are likely aware of their vulnerability. We will follow the standardized and consistent approach in presenting the study material and remuneration for their participation. We will provide a sufficient amount of time and information to consider their involvement in the study.

10.0 Eligibility Screening*

10.1 *Describe screening procedures for determining subjects' eligibility.*

Screening refers to determining if prospective participants meet inclusion and exclusion criteria.

Include all relevant screening documents with your submission (e.g. screening protocol, script, questionnaire).

Screening for inclusion criteria includes a YES response to the following questions:

Is the subject have a current diagnosis of pulmonary hypertension?

Is the subject > 18 years old

Does the subject have access to an electronic device: iPhone, iPad, Android Phone, Laptop?

Is the subject proficient in English?

Screening for exclusion criteria includes a YES response to the following questions:

Has the subject been hospitalized for a psychiatric reason during the past 12 months?

Is the subject hearing-impaired?

Is the subject pregnant? (for female person)

1. Via our referring partners and electronic advertisements (using Research Match, CTSA Hub advertising and social media [e.g., Facebook]), participants will receive an invitation to participate in the study. All communications include the contact information to the PI of the study, email address and phone number.

2. Participants may contact the research coordinator by the included phone number or email address if they want to learn more about the study. A research team member will contact the interested participant and arrange a convenient time for a Zoom meeting.

3. During the Zoom meeting, the research staff member will describe the study and review the consent document. If the participants decides to participate in the study, the research staff will obtain verbal informed consent.

4. The participant will be provided a link (via email or text) to the REDCap database to complete a screening questionnaire.

N/A: There is no screening as part of this protocol.

11.0 Recruitment Methods

N/A: This is a records review only, and subjects will not be recruited. NOTE: If you select this option, please make sure that all records review procedures and inclusion/exclusion screening are adequately described in other sections.

11.1 Describe when, where, and how potential subjects will be recruited.

NOTE: Recruitment refers to how you are identifying potential participants and introducing them to the study. Include specific methods you will use (e.g. searching charts for specific ICD code numbers, Research Participant Groups, posted advertisements, etc.).

There are two ways we will make the study known to potential eligible participants (1) They may hear about the study from their PH doctors during routine clinic visits (2) They may see study flyers in recruiting partners' offices or clinics during their routine care.

Even though we originally proposed that PH doctors send out emails inviting their patients to contact us for potential enrollment, none of the doctors used the letter. They chose to tell their patients about the study verbally, and we only got one referral from RRH. That was the recruitment process we did. As I previously indicated, we are no longer enrolling and will not use it. We only want to complete the study.

Electronic recruitment will include direct email sent using the University at Buffalo's Clinical and Translational Science Institute's (CTSI) Buffalo Research Registry and social media (Facebook). The registry includes names of individuals who have expressed interest in participating in research studies. Facebook-based recruitment will consist of advertisements for the study.

Flyers will be distributed to our referring partners and will be recruited by PH physician referral, self-referral, the use of Buffalo Research Registry, CTSA Hub advertisement, Social Media posts (Facebook), and Research Match. Flyers will be placed by the Research Coordinator at their locations (our referring partners at URMC and RRH). These flyers will be made available in waiting rooms as well as in healthcare professionals' offices.

In both recruitment methods, interested participants will contact the study team directly to initiate the screening as described in section 10.1. None of the referring partners will participate in any screening activities, only referrals.

11.2 Describe how you will protect the privacy interests of prospective subjects during the recruitment process.

NOTE: Privacy refers to an individual's right to control access to him or herself.

The recruitment email and flyer information offers individuals the freedom to participate in the study only if they are interested in doing so.

Screening interviews will take place by Zoom and will be recorded. Recordings will be destroyed after transcripts are created. Participants may take part in the interview at a place and time of their choosing.

Potential research participants will know about the study from PH providers, paper brochures, Buffalo Research Registry, or the ResearchMatch registry. Researchers will make initial contact with potential participants only after a clear indication that they are interested to learn more about the study. These indications are referral from their PH provider, email or phone contact from the participants, or "yes" response through the ResearchMatch registry.

(Please refer to the Recruitment and Enrollment Protocol)

After the Introductory meeting, if prospective participants decline to participate in the study, the research staff will destroy any personal information written down on paper or delete electronic notes. If they express interest and want to meet for the Zoom Consent meeting, we will keep their information as a reference for that meeting. After the Zoom Consent meeting, if prospective participants decline to participate in the study, the research staff will destroy any personal information written down on paper or delete electronic notes immediately. We will only keep the documentation if they agree to participate in the study.

After enrollment, each subject in all phases of the study will be assigned a unique study identification number to be used on all forms. All personally identifiable information will be kept strictly confidential.

Prospective eligible participants will have access to a written version of the consent form that the IRB has approved. There will be instruction for the participant to read the consent form to gain a further, detailed understanding of what the study is about, study participation requirement, and other general information about the human research subject. The participant will then contact the study coordinator to set a convenient time for a virtual meeting or phone call, providing verbal informed consent.

We will keep all records about the recruitment process in password-protected data files according to each institution. Only staff members who are involved in this research will have access to this recruitment record.

11.3 Identify any materials that will be used to recruit subjects.

NOTE: Examples include scripts for telephone calls, in person announcements / presentations, email invitations.

 For advertisements, include the final copy of printed advertisements with your submission. When advertisements are taped for broadcast, attach the final audio/video tape. *NOTE: You may submit the wording of the advertisement prior to taping to ensure there will be no IRB-required revisions, provided the IRB also reviews and approves the final version.*

- 1) Screening protocol; 2) Screening sheet; 3) email invitation script; 4) Advertisement

12.0 Procedures Involved*

12.1 Provide a description of **all research procedures or activities** being performed and when they are performed once a subject is screened and determined to be eligible. Provide as much detail as possible.

NOTE: This should serve as a blueprint for your study and include enough detail so that another investigator could pick up your protocol and replicate the research. For studies that have multiple or complex visits or procedures, consider the addition of a schedule of events table in in your response.

Table 1. Study Procedure

| Procedure | w0-w1 MMPH-1 (Zoom #1) | w1- w2 MMPH-2 (video) | w2-w3 MMPH-3 (video) | w3-w4 MMPH-4 (Zoom #2) | w4- w5 MMPH-5 (video) | w5-w6 MMPH-6 (video) | w6- w7 MMPH-7 (video) | w7-w8 MMPH-8 (video) Zoom #3 |
|------------------------------------|------------------------------|--------------------------------|----------------------------|------------------------------|--------------------------------|----------------------------|--------------------------------|---------------------------------------|
| Instructor-led (min X day) | 60 X 1 | 60 X 1 | 60 X 1 | 60 X 1 | 60 X 1 | 60 X 1 | 60 X 1 | 60 X 1 |
| Self-guided (min X day) | 20 X 6 | 20 X 6 | 20 X 6 | 20 X 6 | 20 X 6 | 20 X 6 | 20 X 6 | 20 X 6 |
| Consent | X | | | | | | | |
| Demographics | X | | | | | | | |
| PAHSS | X | | | X | | | | X |
| EmPHasis-10 | X | | | X | | | | X |
| PHQ-9 | X | | | X | | | | X |
| CAMS-R | X | | | X | | | | X |
| Pain (1-10) | X* | X* | X* | X* | X* | X* | X* | X* |
| Anxiety (1-10) | X* | X* | X* | X* | X* | X* | X* | X* |
| Fatigue (1-10) | X* | X* | X* | X* | X* | X* | X* | X* |
| Dyspnea (1-10) | X* | X* | X* | X* | X* | X* | X* | X* |
| SUS-modified MMPH | | | | | | | | X |
| Interview -MMPH | | | | | | | | X |
| Reminder (via phone or App) - MMPH | X | X | X | X | X | X | X | X |

Note: X* = symptom assessment before and after daily use of MMPH module; PAHSS, Pulmonary Arterial Hypertension Symptoms Scale; EmPHasis-10, Health-related quality of life in pulmonary arterial hypertension; PHQ-9, Patient Health Questionnaire; CAMS-R, Cognitive and Affective Mindfulness Scale-Revised; SUS, System Usability Scale; MMPH, Mindfulness Meditation for Pulmonary Hypertension.

Table 1 outlines the detail and sequence of study intervention. Enrolled participants will receive 60-min-weekly intervention for 8 weeks period; 2 of which will include video conference practice and the other 6 will include audio-video recording of the sessions. During the study period, they will complete self-guided meditation using M-App for 20 min/day.

12.2 Describe what data will be collected.

NOTE: For studies with multiple data collection points or long-term follow up, consider the addition of a schedule or table in your response.

Please refer to Table 1 regarding data that will be collected: symptom presence and severity, health-related quality of life, depressive symptoms, mindfulness score, clinical and demographic data.

12.3 List any instruments or measurement tools used to collect data (e.g. questionnaire, interview guide, validated instrument, data collection form).

Include copies of these documents with your submission.

Response: The following questionnaires will be included in this study:

- Cognitive and Affective Mindfulness Scale-Revised (CAMS-R)
- The Patient Health Questionnaire-9 (PHQ-9)
- Pulmonary Arterial Hypertension Symptom Scale (PAHSS)

- Health-related quality of life in pulmonary arterial hypertension (EmPHass-10)
- System Usability Scale – MMPH (SUS)
- Pain Scale, Anxiety, Fatigue, Dyspnea
-

12.4 *Describe any source records that will be used to collect data about subjects (e.g. school records, electronic medical records).*

We will not use an additional source of records to collect data about subjects in this study.

12.5 *Indicate whether or not individual subject results, such as results of investigational diagnostic tests, genetic tests, or incidental findings will be shared with subjects or others (e.g., the subject's primary care physician) and if so, describe how these will be shared.*

NOT APPLICABLE

12.6 *Indicate whether or not study results will be shared with subjects or others, and if so, describe how these will be shared.*

NOT APPLICABLE

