2.0 Objectives*

2.1 *Describe the purpose, specific aims, or objectives of this research.*

Aim 1: To determine the feasibility and acceptability of the MMPH in community-dwelling URM adults with PH as a symptom self-management tool.

Aim 1a: Feasibility will be assessed by 1) frequency of home practice (> 2/week) and 2) retention rate (>70% of participants remaining at study completion).

Aim 1b: Acceptability will be determined by 1) participants' evaluation of the MMPH program (composite mean System Usability Scale score > 5, scale 1-7), 2) session completion rate (at least 6 of 8 [75% attendance] by the participants retained at the study end), and 3) qualitative thematic analysis of participants.

Aim 2: To determine the clinical impacts of an MMPH program in PH-symptom, anxiety, and depression reduction among community-dwelling URM adults with PH for symptom management.

2.2 *State the hypotheses to be tested, if applicable.*

NOTE: A hypothesis is a specific, testable prediction about what you expect to happen in your study that corresponds with your above listed objectives.

Hypothesis 1: MMPH will meet feasibility and acceptability targets for URM adults with PH

Hypothesis 2: Participants will report reductions in symptom severity of pain, anxiety, dyspnea, and fatigue at the end of the MMPH modules (short-term impacts). Participants will report decreases in the prevalence and intensity of PH-related symptoms, depression, and improved quality of life at the end of the MMPH program (long-term impacts).

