Complementary Health Approach (CHA), such as in-person MBI, has moderate effects in reducing depression and anxiety across chronic health conditions, including PH. However, these benefits were mostly demonstrated among participants who had high adherence to the intervention practice.²⁷ Technology-assisted MBI (TeleMBI) has shown comparable efficacy with in-person MBI among persons with chronic conditions; TeleMBI has the added benefits of cost reduction and ease of implementation.²⁹⁻³¹ TeleMBI for patients with multiple sclerosis via skype shows improvement in HRQOL, depression, anxiety, and sleep disturbance when delivered at a 5:1 ratio of participants and instructor.²⁹ TeleMBI for patients with spinal cord injury with depression and chronic pain was superior to psychoeducational intervention in reducing depressive symptoms, anxiety, pain, and improving HRQOL.³⁰ Online TeleMBI reduces depression and anxiety significantly compared to the control group among pregnant women with high depressive symptoms.³¹ The use of TeleMBI via Mobile-APP among post ICU patients has comparable impacts on depression, anxiety, and post-traumatic distress symptoms to telephone-based mindfulness delivery.³² This pilot RCT study is advancing to a large-scale study to implement TeleMBI Mobile-APP to treat post ICU symptoms. While mobile- and in-person MBI have comparable efficacy, we postulate that the mobile-MBI has the advantages of user-activated, "as needed" delivery, consistent dose delivery, and ease of use for symptom management for adults with PH. Clearly, given these advantages of mobile-MBI and in keeping with the social distancing demand of the current COVID-19 pandemic, it is imperative to test MMPH mobile MBI for PH in URM communities to address our research aims.

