5.0 Study Design*

5.1 *Describe and explain the study design (e.g. case-control, cross-sectional, ethnographic, experimental, interventional, longitudinal, observational).*

This study will engage community-dwelling URM adults with PH living in the United States. We will use a two-group comparative study design where waitlisted participants will serve as controls. Considering a 20% attrition rate in a behavioral health intervention study, we aim to enroll a total of 20, with at least 16 participants to address study aims (8-10 in each Group).³⁴ As a pilot study, power analysis is not necessary. Statistical analysis will include descriptive statistics, mixed-effect modeling for repeated measures, and within-group and between-groups comparisons using t-tests or Wilcoxon signed-rank test as appropriate and Cohen's d effect size calculation. Multi-time data collection will be done via daily mobile-APP use.

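### The four 1-10 symptom ratings exist only around module use, so the short-term impact has no control and no listed anxiety-specific measure gives a between-group comparison

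*Combined protocol and SAP*

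**What the plan says.** Section 5.1 sets out a "two-group comparative study design where waitlisted participants will serve as controls". Table 1 in Section 12.1 schedules PAHSS, EmPHasis-10, PHQ-9 and CAMS-R at three points (the first, fourth and eighth program weeks). Pain, anxiety, fatigue and dyspnea appear every week, but only with an asterisk that the table note defines as "symptom assessment before and after daily use of MMPH module". The table has no separate schedule for the waitlist.

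Aim 2 (Section 2.1) is "To determine the clinical impacts of an MMPH program in PH-symptom, anxiety, and depression reduction". Hypothesis 2 (Section 2.2) begins: "Participants will report reductions in symptom severity of pain, anxiety, dyspnea, and fatigue at the end of the MMPH modules (short-term impacts". In the instrument list of Section 12.3, the entry "Pain Scale, Anxiety, Fatigue, Dyspnea" is the only one named for anxiety. The summary of data in Section 12.2 mentions depressive symptoms but not anxiety.

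Section 19.1 assigns the effect of the App on outcomes to a paired t-test and repeated-measures ANOVA. It also plans a post-intervention comparison of clinical outcomes between groups, without listing the outcomes.

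On how modules are used, Section 12.1 says that participants are scheduled for daily practice: "they will complete self-guided meditation using M-App for 20 min/day". Table 1 gives 20 minutes on 6 days a week, with reminders every week. Section 4.1 postulates that "the mobile-MBI has the advantages of user-activated" and as-needed use, and Aim 1a counts more than 2 home practices a week as feasible.

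**The concern.** The trial has a control group, but the ratings behind the short-term hypothesis cannot be taken in it. People often feel somewhat better after sitting quietly for 20 minutes, after being asked to expect benefit, or simply later in the day. A before/after fall contains all of these and cannot be separated from a module effect by a paired test. If participants also tend to practise on their worse days, part of the fall is regression to the mean.

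Preliminary impact on symptom management is part of the primary objective (Section 1.0), so the fall would be read as evidence about the program. Section 4.1 says that the earlier single-group pilot already reported pre-post session reductions in the same four symptoms. As scheduled, this trial repeats that uncontrolled measure, and its control group adds nothing to it. For anxiety, the gap reaches a named aim.

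**Working it through.** **1. The plan's own figure.** Section 5.1 enrols 20 to retain 16 at 20% attrition: 16 / (1 - 0.20) = 20, which reproduces. That leaves 8 to 10 per group, the number used below. No SD, correlation or effect size is stated, so those values are assumptions.

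**2. Which group has which data.**

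| Measure | MMPH group | Waitlist while waiting |
|---|---|---|
| PAHSS, EmPHasis-10, PHQ-9, CAMS-R | three fixed points | no separate schedule, but possible at the same points |
| Pain, anxiety, fatigue, dyspnea (1-10) | before and after each module | not possible as defined, since there is no module |

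If waitlisted participants receive the program later, their ratings would then be treated data as well, not a control.

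**3. Regression to the mean with no true effect, per session.** Suppose a module is opened when a symptom is exactly 1 SD above the person's own mean, and the before and after ratings have within-person correlation r. The expected fall is (1 - r) SD. With the first rating fixed, the SD of the change is sqrt(1 - r²).
- r = 0.5: 0.5 / sqrt(0.75) = 0.58
- r = 0.8: 0.2 / sqrt(0.36) = 0.33

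Using the unconditional SD, sqrt(2(1 - r)), would give 0.50 and 0.32. It does not match a start fixed at +1 SD.

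**4. How this depends on which days are used.** If modules are used on the worst fraction f of days, the expected fall is SD × (1 - r) × φ(c) / f, with c the normal quantile at 1 - f. The table assumes a within-person SD of 1.5 points and r from 0.9 to 0.5. The last column comes from a simulation with 56 independent days, 2,000 runs and n = 8 or 10. It is the chance that a two-sided 5% paired t-test on person means shows a significant improvement.

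| Days used | Fall, points | Significant improvement |
|---|---|---|
| all scheduled days | 0 | 2-3% (nominal 2.5%) |
| all but the best day in 7 | 0.04-0.20 | 17-77% |
| worst 3 days in 7 | 0.14-0.69 | 71-100% |

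Three days a week is the fewest that meets the target of more than 2. The simulation gives every person the same expected change. Real variation between people would lower the percentages in the lower two rows, so they show a mechanism and are not a forecast.

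**5. What a between-group comparison can deliver.** The 95% half-width for a standardised difference is about t × sqrt(2/n).
- n = 8 per group: 2.145 × 0.500 = 1.07 SD
- n = 10 per group: 2.101 × 0.447 = 0.94 SD

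The difference detectable with 80% power at two-sided 5% is 1.51 SD with 8 per group and 1.32 SD with 10.

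**The case against.** The strongest reply is that the regimen is scheduled. Sections 6.1, 12.1 and 13.2 prescribe daily practice, and Table 1 has a reminder in every week. The as-needed idea comes from one Background sentence that also claims consistent dosing, and no section tells participants to open a module when symptoms are bad. The target of more than 2 practices a week allows skipped days but does not show that better days are the ones skipped. All of this stands. A reader might infer that the ratings would be expected to fall with no effect at all. The documents do not support that: the artefact is zero under the written schedule, and its size cannot be known from the text.

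A reader might also infer that the module rating is the only anxiety outcome. The PAHSS items are not in the documents, so an anxiety item, or items on the other three symptoms, cannot be excluded. What can be said is that no other listed instrument is named for anxiety.

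The endpoints in Section 3.1 are PAHSS and EmPHasis-10, not these ratings, and an acute before/after measure is a recognisable choice in a 20-person pilot. That lowers the stakes. It does not justify calling an uncontrolled change an impact.

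Finally, fixed-time ratings do not control the module-level change, and the between-group estimate will be imprecise. Both are true, and both limit what the fix can claim.

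**Conclusion.** The point holds on structure, which needs no assumptions. As scheduled, the waitlist has no ratings of the four symptoms, so the short-term part of Hypothesis 2 is an uncontrolled within-person change. Anxiety in Aim 2 has no between-group comparison from any listed anxiety-specific measure. Rest, expectation and time of day remain uncontrolled even with perfect adherence to the schedule.

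Regression to the mean is a conditional addition. It runs from zero, if use follows the schedule, to about 0.33 to 0.58 paired SD units, if modules are opened at +1 SD with a correlation of 0.8 to 0.5. The trigger, the correlation and normality are all assumptions. This should be corrected, but it does not undermine the feasibility aims.

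**What to change.** - Add the same four 1-10 items to the existing questionnaires at weeks 0, 4 and 8 in both groups, and state in Table 1 that the waitlist completes them.
- Base Aim 2 statements on anxiety, pain, fatigue and dyspnea on the between-group estimate with its 95% confidence interval. Say in advance that it will be imprecise at 8 to 10 per group.
- Report the module before/after change as uncontrolled description, not as impact, because the added ratings do not control it.
- Show prompted and as-needed sessions separately only if the App already logs how a session was started. No section describes such logging.

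Cost: four single items at three existing occasions, 4 × 3 = 12 extra responses per participant and roughly a minute each time. The downside is slightly longer forms and a more modest short-term claim.

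Timing matters. Section 11.1 says that the team is no longer enrolling, although Section 7.2 still looks ahead to the enrolment goal. The added items help only participants whose time points remain, and missed baselines cannot be recovered. The reporting change can be made at any time before analysis. Label: cheap improvement.
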